# 6.1.3 Subgroups

For mITT subjects, the following efficacy subgroups are of interest:

- Age:  $< 40, \ge 40 \text{ years}$
- Sex: female, male
- Race: White, Black or African American, Other including Asian, Asian
- Ethnicity: Hispanic or Latino, Not Hispanic or Latino
- Baseline body mass index (BMI; kg/m^2):  $< 25, \ge 25$  to  $< 30, \ge 30$
- Aura at on-study migraine attack onset: yes, no
- Historical number of moderate or severe migraine attacks per month: < median, ≥ median, where the median is calculated overall across treatment groups combined for mITT subjects and rounded to an integer.
- Triptan non-responder: yes, no (see Section 7.2).

Subgroup analyses will be performed for the co-primary efficacy endpoints only. Efficacy subgroup tables will present results by subgroup level for subjects with non-missing subgroup level data, unless specified otherwise.

Subgroup levels may be redefined or combined based on the availability of data.

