#### 6.3 Efficacy

Efficacy analyses will be based on mITT subjects by as-randomized treatment group only (excluding All BHV-3500 and overall).

Treatment comparisons of binary endpoints will be stratified by prophylactic migraine medication use at randomization except within subgroups. If a single cell has sparse data (< 5 subjects), then the analysis will be performed pooled across strata.

All CIs will be two-sided. In treatment comparisons of binary endpoints, CIs will be based on a normal approximation to the binomial distribution using asymptotic standard error (ASE). In descriptive analyses of binary endpoints, exact Clopper-Pearson CIs will be used. Otherwise, CIs for continuous endpoints will be based on the normal distribution.

A by-subject listing of eDiary migraine characteristics will be provided for randomized subjects that displays parameters listed in Section 7.6.3.2 at migraine attack onset and over time post-dose. The rescue medication start date/time and time to rescue medication use in hours will also be included (see Sections 6.3.4.3 and 7.3); data collected on or after the rescue medication start date/time will be flagged.

Post-dose efficacy data will be slotted into analysis windows automatically by the eDiary (see Section 7.6.3.2). All efficacy endpoints will be assessed using analysis windows, unless specified otherwise.

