#### **Principal Analyses**

Pain freedom outcomes at 2 hours post-dose will be summarized by treatment group (see Section 6.3.5.2). Outcomes will be summarized analogously for each subgroup level of all efficacy subgroups of interest specified in Section 6.1.3.

The percentages of subjects with pain freedom at 2 hours post-dose will be compared pairwise between each BHV-3500 treatment group and placebo using Cochran-Mantel-Haenszel (CMH) tests stratified by prophylactic migraine medication use at randomization (yes, no). In these analyses, the NC=F and RM=F methods will be applied. The following statistics will be presented:

- Response rate (i.e., "n/N" and percentage), ASE, and 98.3% CI by randomization stratum for each treatment group
- Overall response rate (i.e., "n/N" and percentage), ASE, and 98.3% CI for each treatment group
- Percentage difference between treatment groups (BHV-3500 placebo), ASE, 98.3% CI, and p-value by randomization stratum
- Stratified percentage difference between treatment groups (BHV-3500 placebo), ASE, 98.3% CI, and p-value.

The stratified percentage difference between each BHV-3500 treatment group and placebo will be tested at a Bonferroni-corrected alpha level of 0.0167. A BHV-3500 treatment group will be considered to be superior to placebo for this co-primary endpoint if the p-value for the stratified percentage difference is < 0.0167.

The principal analysis will be repeated unstratified for each subgroup level of all efficacy subgroups of interest specified in Section 6.1.3.

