### 7.1.1.1 Time-to-Event Tables and Plots

Time-to-event endpoints will be summarized with KM tables displaying the following at each time interval:

- Number of subjects at risk, defined as those who did not have the event just prior to the start of the interval and who were not censored prior to the interval
- Number of subjects with events, defined as those who had the event for the first time during the interval
- Number of subjects censored, defined as those who did not have the event and whose censoring date/time is in the interval
- Cumulative probability of having the event with lower and upper CI limits, based on the KM product limit method.

Time-to-event endpoints will also be summarized with corresponding KM plots displaying 100 times the cumulative probability of having the event on the y-axis and time on the x-axis, including the number of subjects at risk at each time point below the x-axis.

Time-to-event distributions of endpoints will be summarized with the following descriptive statistics: number and percentage of subjects with events; number and percentage of subjects censored in or before the last time interval; number and percentage of subjects censored in the last time interval; median time to event with CI using the method of Brookmeyer and Crowley.

CI levels will be 98.3% for efficacy endpoints and 95% for all other endpoints.

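### The SAP sets no minimum size and no small-sample interval for subgroup differences, so a small level could show a 98.3% interval that is too narrow or has zero width

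*SAP*

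**What the plan says.** SAP 6.3 (Efficacy) fixes the interval method: "In treatment comparisons of binary endpoints, CIs will be based on a normal approximation to the binomial distribution using asymptotic standard error (ASE". It also says "All CIs will be two-sided", and it reserves exact Clopper-Pearson intervals for descriptive summaries. It attaches no sample-size condition to the rule for comparisons.

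Section 6.3.3.1 lists a percentage difference, its ASE, a 98.3% CI and a p-value among the statistics for pain freedom at 2 hours. It then adds: "The principal analysis will be repeated unstratified for each subgroup level of all efficacy subgroups of interest specified in Section 6.1.3". Section 6.3.3.2 does the same for MBS freedom and adds MBS at attack onset as a further subgroup. Each subgroup level therefore receives three dose-versus-placebo intervals on each co-primary endpoint.

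Two provisions deal with thin data:

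- SAP 6.3: "If a single cell has sparse data (< 5 subjects), then the analysis will be performed pooled across strata".
- SAP 6.1.3: "Subgroup levels may be redefined or combined based on the availability of data".

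Section 6.1.3 also lists the race levels: "Race: White, Black or African American, Other including Asian, Asian". Asian subjects are thus counted in a combined level and again in a level of their own.

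**The concern.** The normal-approximation (Wald) interval for a difference in proportions depends on the observed rates being a good guide to the variance. That fails when an arm has only a few responders, as it would in a small level with pain freedom of 12% to 22%. If neither arm has a responder, the estimated standard error is zero and the interval runs from 0 to 0.

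Neither provision reliably prevents this. Pooling strata changes nothing in an analysis that is already unstratified. Combining levels is permitted but not required, has no threshold, and leaves the interval method as it is.

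At stake is how subgroup tables are read. They are used to judge whether the effect is consistent, and an interval that is too short, or has no width, presents scarce data as precise data.

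**Working it through.** **Inputs.** From SAP 5: about 380 mITT subjects per arm, pain freedom 22% v 12%, MBS freedom 45% v 32%, alpha 0.0167. From SAP 6.3.3.1: 98.3% intervals, so z = 2.387. Level sizes are not given. As an assumption, a level holding 2% to 5% of an arm has 380 × 0.02 = 7.6 to 380 × 0.05 = 19 subjects, that is about 8 to 19 per arm. Equal arm sizes within a level are also assumed.

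**The plan's own figure first.** Power = Φ[(Δ − z₀·SE₀)/SE₁], where SE₀ is the pooled and SE₁ the unpooled standard error and z₀ = 2.393 for two-sided alpha 0.0167.

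- Pain freedom: (0.10 − 2.393 × 0.02725)/0.02701 = 1.29, power 90.1%.
- MBS freedom: (0.13 − 2.393 × 0.03530)/0.03499 = 1.30, power 90.3%.
- Joint, if independent: 0.901 × 0.903 = 81.4%.

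These agree with the stated 90%, 90% and roughly 80%.

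**Wald interval.** d ± 2.387 × √[p₁(1−p₁)/n + p₂(1−p₂)/n], using the observed rates p₁ and p₂, with d = p₁ − p₂. Exact coverage is the sum, over all pairs of responder counts, of the product of the two binomial probabilities wherever the interval contains the true difference.

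| Per arm | Pain freedom 22% v 12%: coverage | Zero width | MBS freedom 45% v 32%: coverage | Zero width |
|---|---|---|---|---|
| 8 | 93.6% | 4.9% | 95.3% | 0.05% |
| 10 | 95.3% | 2.3% | 96.3% | 0.01% |
| 20 | 97.3% | 0.05% | 97.6% | about 0 |
| 50 | 97.9% | about 0 | 98.0% | about 0 |
| 380 | 98.3% | about 0 | 98.2% | about 0 |

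At 10 per arm, pain-freedom non-coverage is 100 − 95.3 = 4.7%, against a nominal 1.7%.

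**Zero width by hand.** With 10 per arm, no responder in either arm has probability 0.78¹⁰ × 0.88¹⁰ = 0.0834 × 0.2785 = 2.3%. If both rates are 12%, it is 0.88²⁰ = 7.8%.

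**Equal rates.** With 12% in both arms, coverage is 99.2% at 8 per arm and 98.6% at 10. The 0-to-0 interval then happens to contain the true difference of zero, so coverage does not reveal the defect.

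**Score interval.** Miettinen-Nurminen coverage for pain freedom at 22% v 12% is 99.8% at 8, 99.5% at 10 and 98.7% at 20 per arm. For MBS freedom it is 98.7% at 10. For 0/10 v 0/10 the upper limit solves 9.5δ/(1−δ) = 2.387² = 5.70, so δ = 5.70/15.20 = 0.375. The interval is about −37.5 to +37.5 points, where Wald gives 0 to 0.

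**The case against.** The strongest reply is that nobody has shown any level to be small. Neither document gives a subgroup size. The Other race level already pools several categories (SAP 6.2.4.1), and nothing suggests that triptan non-responders are rare. Age, sex, ethnicity, BMI, aura and the median split of attack frequency are not shown to be small either. This stands. Only the separate Asian level is a plausible case, and 10 per arm would be 10/380 = 2.6% of an arm.

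Second, a reader might infer that subgroup intervals will cover far less than 98.3%. The figures do not support that over the assumed range: with equal arms the shortfall is under 5 points at 8 per arm and about 1 point at 20. A large loss needs something like 5 per arm, where pain-freedom coverage is 83.8%, and that is 1.3% of an arm. MBS freedom is milder and almost never gives zero width.

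Third, 6.1.3 lets the sponsor combine thin levels, and the table shows n/N, so a 0-to-0 interval would sit beside 0/10 v 0/10 and look degenerate. That softens the effect but does not remove it. Combining is optional and has no threshold, and an interval that is too short without being degenerate carries no such warning.

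Fourth, subgroups lie outside the testing hierarchy in 6.1.2. This also stands and limits the importance of the point.

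**Conclusion.** The gap is real and minor. The SAP prescribes a large-sample interval for every subgroup difference, sets no minimum level size, and has no safeguard that must apply in unstratified analyses. Whether it does harm depends on level sizes that the documents do not give.

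If a level has 8 to 20 per arm, with equal arms and the SAP's planning rates, the nominal 98.3% interval is short of its level by 4.7 to 1.0 points for pain freedom and by 3.0 to 0.7 points for MBS freedom. Unequal arms can be worse: 10 active v 15 placebo gives 90.5% for pain freedom and 96.4% for MBS freedom. Zero-width intervals are mainly a pain-freedom problem at about 10 per arm or fewer.

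It would be wrong to infer that the primary analysis is at risk. At 380 per arm the interval performs as intended, and no formal conclusion rests on a subgroup result.

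**What to change.** Add one sentence to SAP 6.3: confidence intervals for unstratified subgroup differences use the Miettinen-Nurminen score method, while the stratified overall difference and the individual randomisation strata keep the ASE interval. State in the same place whether the subgroup p-values stay as they are. A numeric threshold in 6.1.3 for combining or not reporting a level would be a workable alternative.

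The work is one sentence and one software option. There are two modest drawbacks. Score intervals are slightly wide in the smallest levels (about 99.5% coverage at 10 per arm for pain freedom). The subgroup tables would also use a different method from the primary table, which needs a footnote. Making the choice before unblinding avoids having to defend a change of method after seeing a degenerate interval.

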# 6.3.1 Principal Analysis Methods of Handling Missing Data and Intercurrent Events

Methods of handling missing data in principal analyses of binary efficacy endpoints are defined as follows:

- Non-Completer = Failure (NC=F): Subjects with missing data at a single time point will be classified as failures. This missing data imputation method will be applied to endpoints based on data from a single time point (e.g., co-primary endpoints at 2 hours post-dose).
- Non-Completer With Missing Data at More Than 1 Time Point = Failure (NC1=F): Subjects with missing data at > 1 time point post-dose in a specified time period will be classified as failures. This missing data imputation method will be applied to endpoints that are based on data from multiple time points (e.g., secondary endpoint of sustained pain freedom from 2 to 24 hours post-dose).
- Non-Completer = Missing (NC=M): Subjects with missing data at a single time point will be excluded from the analysis. This missing data exclusion method will be applied to endpoints based on data from a single time point (e.g., co-primary endpoints at 2 hours post-dose).

The intercurrent event of rescue medication use will be handled using Rescue Medication = Failure (RM=F), i.e., subjects who take rescue medication will be classified as failures for all efficacy evaluations that are reported at or after taking rescue medication, i.e., (1) rescue medication start date/time  $\leq$  eDiary finding date/time if start time is not missing, or (2) rescue medication start date  $\leq$  eDiary finding date if start time is missing; see Sections 6.2.5.2 and 7.3). This method will apply to all efficacy analyses, except the secondary endpoint of rescue medication use within 24 hours post-dose.

#### 6.3.2 Missing Efficacy Data

Missing efficacy data will be summarized by treatment group as the number and percentage of mITT subjects in the following categories:

- Missing pain data at each time point from 15 minutes through 48 hours post-dose. These categories are not mutually exclusive because subjects may have missing data at multiple time points.
- Number of time points with missing pain data from 2 hours to 48 hours post-dose: 0 (i.e., no missing pain data), 1, 2, 3, 4, 5, 6, 7. These categories are mutually exclusive.
- Missing data for the following efficacy parameters at 2, 24, and 48 hours post-dose: pain level, nausea status, phonophobia status, photophobia status, and functional disability level.

In addition, missing pain data at 2 hours post-dose will be summarized by subgroup level for each treatment group and overall for all subgroups specified in Section 6.1.3 plus the following subgroups:

- Pain level at on-study migraine attack onset (moderate or severe)
- MBS at on-study migraine attack onset (nausea, phonophobia, or photophobia)
- Rescue medication use: yes, no.

# 6.3.3 Primary Efficacy Endpoints

Both co-primary efficacy endpoints will be evaluated for mITT subjects.

A by-subject listing of pain freedom and MBS freedom outcomes at each post-dose time point will be provided for randomized subjects that includes prophylactic migraine medication use at randomization, rescue medication start date/time (see Section 7.3), time to rescue medication start date/time in hours (see Section 6.3.4.3), pain level at on-study migraine attack onset, MBS at on-study migraine attack onset, and reason for exclusion from the mITT population sample (see Section 6.2.1). Missing data and complete cases (see Section 6.3.5.2) will be flagged at each time point for each endpoint. See Section 6.3.5.2 for efficacy outcomes.

#### 6.3.3.1 Pain Freedom at 2 Hours Post-Dose

Pain freedom is defined as having a pain level of none at a single time point post-dose.

For the co-primary endpoint, subjects who meet both of the following criteria will be classified as responders:

- Pain level of none at 2 hours post-dose, i.e., in the 2-hour post-dose analysis window
- No intervening rescue medication taken at or before 2 hours post-dose, i.e., rescue medication start date/time missing or > {eDiary finding date/time in the 2-hour post-dose analysis window}.

Subjects who are not classified as responders and have any of the following will be classified as failures:

- Intercurrent event: Rescue medication taken at or before 2 hours post-dose (RM=F), i.e., (rescue medication start date/time study drug start date/time) ≤ 135 minutes, the upper bound of the 2-hour post-dose analysis window (see Section 7.5)
- Mild, moderate, or severe pain at 2 hours post-dose, i.e., in the 2-hour post-dose analysis window
- Missing pain level at 2 hours post-dose (NC=F), i.e., in the 2-hour post-dose analysis window.

#### **Principal Analyses**

Pain freedom outcomes at 2 hours post-dose will be summarized by treatment group (see Section 6.3.5.2). Outcomes will be summarized analogously for each subgroup level of all efficacy subgroups of interest specified in Section 6.1.3.

The percentages of subjects with pain freedom at 2 hours post-dose will be compared pairwise between each BHV-3500 treatment group and placebo using Cochran-Mantel-Haenszel (CMH) tests stratified by prophylactic migraine medication use at randomization (yes, no). In these analyses, the NC=F and RM=F methods will be applied. The following statistics will be presented:

- Response rate (i.e., "n/N" and percentage), ASE, and 98.3% CI by randomization stratum for each treatment group
- Overall response rate (i.e., "n/N" and percentage), ASE, and 98.3% CI for each treatment group
- Percentage difference between treatment groups (BHV-3500 placebo), ASE, 98.3% CI, and p-value by randomization stratum
- Stratified percentage difference between treatment groups (BHV-3500 placebo), ASE, 98.3% CI, and p-value.

The stratified percentage difference between each BHV-3500 treatment group and placebo will be tested at a Bonferroni-corrected alpha level of 0.0167. A BHV-3500 treatment group will be considered to be superior to placebo for this co-primary endpoint if the p-value for the stratified percentage difference is < 0.0167.

The principal analysis will be repeated unstratified for each subgroup level of all efficacy subgroups of interest specified in Section 6.1.3.

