### 2.2 Randomization Methodology

Per protocol, subjects in this study may be randomized only once.

The study will randomize approximately 1,600 subjects. The subjects will be randomized in a 1:1:1:1 ratio across 4 treatment groups (BHV-3500 5 mg, BHV-3500 10 mg, BHV-3500 20 mg, or placebo); see Figure 1. The randomization will be stratified by prophylactic migraine medication use (yes or no).

[figure not shown]

Figure 1: Study Schematic

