#### 5 SAMPLE SIZE AND POWER

If 95% of the 400 subjects randomized to each treatment group treat a migraine on study, then there will be roughly 380 mITT subjects in each treatment group.

If the true response rates for pain freedom at 2 hours are 22% and 12% in the BHV-3500 and placebo groups, then a chi-square test at alpha=0.0167 will have 90% power. Similarly, if the true response rates for MBS freedom at 2 hours are 45% and 32% in the BHV-3500 and placebo groups, then a chi-square test at alpha=0.0167 will have 90% power. Under the assumption that the endpoints are independent, the power for both endpoints jointly is roughly 80%.

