# 6.1.2 Type I Error Control

Type I error will be controlled by a hierarchical gate-keeping procedure. First, the family of two co-primary endpoints will be tested. In particular, each BHV-3500 treatment group will be tested for superiority against placebo at a Bonferroni corrected alpha=0.0167 level for both co-primary endpoints. If both co-primary endpoint tests are determined to be significant for a BHV-3500 treatment group versus placebo, then the secondary endpoints will be tested for that BHV-3500 treatment group versus placebo using a hierarchical gate-keeping procedure, with each test in the hierarchy conducted at alpha=0.0167.

The secondary endpoints will be tested in the order shown in Section 1.2.2.

If a test in the hierarchy is not significant, then any further tests on endpoints in the sequence will have p-values presented only for descriptive purposes, and no conclusions will be drawn from those results.

For exploratory endpoints, no attempt will be made to adjust for multiplicity. Any exploratory endpoints for which p-values are produced will be evaluated at an unadjusted two-sided alpha level of 0.05 and presented only for descriptive purposes.

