#### **Sensitivity Analyses**

Sensitivity analyses will include the following:

- Complete cases: The principal analysis will be repeated using NC=M, i.e., subjects who have missing pain level in the 2-hour post-dose analysis window are excluded. First, the RM=F method of handling intervening rescue medication use will be applied. Next, subjects with missing data in the 2-hour analysis window will be excluded. The same statistics as the principal analysis will be presented.
- Multiple imputation: The principal analysis will be repeated using the copy from reference multiple imputation approach with m=20 imputations to impute missing pain data at 2 hours post-dose. The fully conditional specification (FCS) method is used with a generalized logit distribution. Covariates may include prophylactic migraine medication use at randomization (yes or no), sex, pain level at on-study migraine attack onset (moderate or severe), historical number of moderate to severe migraine attacks per month (< median, ≥ median), and MBS at on-study migraine attack onset (nausea, phonophobia, or photophobia). First, the RM=F

method of handling intervening rescue medication use will be applied. Next, missing data in the 2-hour post-dose analysis window will be imputed for subjects who are not missing any of the covariates (subjects missing any of the covariates will be considered failures). The same statistics as the principal analysis will be presented.

• Varying response rate imputation: The principal analysis will be repeated by imputing missing pain data at 2 hours post-dose in each treatment group with varying response rates over the range of 0%, 10%, 20% and 30%. First, the RM=F method of handling intervening rescue medication use will be applied. Next, missing data in the 2-hour post-dose analysis window will be imputed. The following statistics will be presented: stratified percentage difference between treatment groups (BHV-3500 – placebo), ASE, 98.3% CI, and p-value.

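### The co-primary comparisons adjust only for prophylactic medication use; adding pain level at attack onset, known for every mITT subject, would give a small gain in precision and protection against chance imbalance

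*SAP*

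**What the plan says.** The principal analysis of pain freedom (SAP 6.3.3.1) uses CMH "tests stratified by prophylactic migraine medication use at randomization (yes, no"), and 6.3.3.2 does the same for MBS freedom. Protocol 9.4.1 names the same single factor, which is also the only randomisation stratum (SAP 2.2).

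Moderate or severe pain at onset of the treated attack is a condition of mITT membership (SAP 3), so the level is known for everyone analysed. The SAP tabulates it by arm (6.2.4, 6.2.4.6), includes it in the co-primary listing (6.3.3) and uses it as a subgroup when summarising missing 2-hour pain data (6.3.2). In the multiple-imputation sensitivity analysis, "pain level at on-study migraine attack onset (moderate or severe") appears in a list of covariates that may be included. It is not among the efficacy subgroups (6.1.3), and no principal or sensitivity analysis adjusts the treatment comparison for it.

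SAP 6.3 adds a rule for binary comparisons generally: "If a single cell has sparse data (< 5 subjects), then the analysis will be performed pooled across strata". It does not define a cell.

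**The concern.** Pain freedom at 2 hours is a later reading on the same four-point scale as the onset level. A subject who starts at severe has further to go to reach none, so an association with outcome is a reasonable expectation. Leaving a prognostic baseline variable out of the comparison gives up some precision. It also leaves the estimate exposed to whatever severity mix chance produces.

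Severity could not have been a randomisation stratum, because the attack may come up to 45 days after randomisation. Adjustment in the analysis is therefore the only route. One placebo arm serves all three comparisons, so an unlucky placebo mix would move all three in the same direction. The baseline table would show it, but no pre-specified analysis would answer it. Success for a dose needs both co-primary endpoints, with joint power put at roughly 80%, so small gains on each have some value.

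**Working it through.** **Inputs from the documents**
- Alpha: "each BHV-3500 treatment group will be tested for superiority against placebo at a Bonferroni corrected alpha=0.0167 level for both co-primary endpoints" (SAP 6.1.2). Taken as two-sided, because "All CIs will be two-sided" (SAP 6.3) and the 98.3% level matches; z = 2.393.
- Size: "there will be roughly 380 mITT subjects in each treatment group" (SAP 5), so n = 380. Subjects are "randomized in a 1:1:1:1 ratio across 4 treatment groups" (SAP 2.2), so each dose against placebo is 1:1.
- Rates: "true response rates for pain freedom at 2 hours are 22% and 12% in the BHV-3500 and placebo groups" (SAP 5); for MBS freedom, 45% and 32%.

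**Step 1: the plan's own power.** Chi-square with pooled variance: power = Φ[(Δ − z·SE0)/SE1], where SE0 = √[2p̄(1−p̄)/n] and SE1 = √{[p1(1−p1) + p0(1−p0)]/n}.
- Pain freedom: p̄ = 0.17, SE0 = 0.02725, SE1 = 0.02701; (0.10 − 2.393 × 0.02725)/0.02701 = 1.288, power 90.1%.
- MBS freedom: p̄ = 0.385, SE0 = 0.03530, SE1 = 0.03498; (0.13 − 2.393 × 0.03530)/0.03498 = 1.301, power 90.3%.
- Joint, if independent: 0.901 × 0.903 = 81.4%.

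The stated 90%, 90% and roughly 80% reproduce with no severity adjustment. With SE1 alone (unpooled), pain freedom gives Φ(0.10/0.02701 − 2.393) = 90.5%, the baseline for step 2.

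**Step 2: precision gained for pain freedom.** The severe share q and the severity-specific rates are assumptions. Take q = 30-40%, placebo 14-16% (moderate) against 5-7% (severe), and active 25-28% against 13-15%. Hold the overall rates at 22% and 12%, and let d1 and d0 be the moderate-minus-severe gaps on active and placebo. Given the stratum sizes, stratifying removes q(1−q)(d1² + d0²) from the total 0.22 × 0.78 + 0.12 × 0.88 = 0.2772.

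| | q | d0 | d1 | Removed | Variance reduction | Power |
|---|---|---|---|---|---|---|
| Weakest | 0.30 | 0.07 | 0.10 | 0.21 × 0.0149 = 0.0031 | 1.1% | 90.8% |
| Strongest | 0.40 | 0.11 | 0.15 | 0.24 × 0.0346 = 0.0083 | 3.0% | 91.4% |

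In subjects this is 380/(1 − 0.011) − 380 ≈ 4 to 380/(1 − 0.030) − 380 ≈ 12 per arm.

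**Step 3: chance imbalance.** The SD of the between-arm difference in severe share is √[2q(1−q)/380], or 3.3 points at q = 0.30 and 3.6 at q = 0.40. A 5-point imbalance is about 1.4-1.5 SD. It shifts the unadjusted difference by about 0.05 × (d1 + d0)/2: 0.05 × 0.085 = 0.4 points to 0.05 × 0.13 = 0.65 points, against a planned 10.

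**Step 4: wider assumptions, including MBS freedom.** Assume 20-50% severe and an odds ratio of response (severe against moderate) of 0.8 to 0.25, the same in both arms. With the step 1 power as baseline:

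| | Variance reduction | Power | Shift from a 1.96-SD imbalance |
|---|---|---|---|
| Pain freedom | 0.1-6.0% | 90.1% to 90.1-91.9% | 0.2-1.3 points |
| MBS freedom | 0.2-10.2% | 90.3% to 90.4-93.4% | 0.3-2.2 points |

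**Step 5: validity.** In simulated trials (200,000 replicates per setting; 30% and 50% severe; odds ratios 0.67, 0.5 and 0.33), type I error was about 0.016-0.017 with or without severity.

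**Step 6: the pooling rule.** Assume 20% prophylactic use, 35% severe and 6% placebo response in severe attacks. The prophylactic/severe placebo group then has 380 × 0.20 × 0.35 ≈ 27 subjects and 27 × 0.06 ≈ 1.6 responders. If a cell means a cell of the 2×2 table, the rule would pool the strata and undo the adjustment.

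**The case against.** The strongest reply is that nothing is broken. The analysis stratifies by the one randomisation factor, protocol and SAP agree, the stated power is met and the error rate holds. Randomisation balances severity in expectation, and the test already allows for chance imbalance. All of that stands, and it limits this point to an efficiency recommendation.

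A reader might infer from the imputation model that the SAP itself declares severity a predictor of outcome. It does not: severity is one of several covariates that may be used to impute missing data, and neither document gives a prognostic strength. A reader might also assume that the level is always recorded before dosing. SAP 7.6.3.2 shows otherwise: subjects who took study drug before using the eDiary report the level afterwards, for the time of dosing.

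The argument about starting further from none concerns pain. For MBS freedom the association is less direct and its size is unknown.

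The practical objections have force too. The pooling rule covers binary comparisons generally, and the secondary endpoints borrow the 6.3.3.1 methods, so an unrestricted change would spread. Pain relapse, analysed only in subjects pain-free at 2 hours, would be hit hardest: on the step 2 assumptions placebo has about 6-11 severe-attack responders in all (380 × 0.30 × 0.05 to 380 × 0.40 × 0.07). By-stratum intervals under a normal approximation would also be unreliable in such small groups. These are reasons to confine the change, not to drop it.

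**Conclusion.** The point holds as a small improvement. Both co-primary comparisons leave out a baseline value that is available for every analysed subject and plausibly related to outcome. On the stated assumptions, adjusting cuts the pain-freedom variance by about 1.1-3.0%, adds roughly 0.3-0.9 points of power, and removes a shift of about 0.4-0.65 points should a 5-point imbalance occur. The MBS-freedom gain could be smaller or larger.

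These sizes rest on an assumed severe share and assumed severity-specific rates. If severity is only weakly prognostic, the gain is close to nil. The documents do not support reading the omission as a source of bias, an inflated error rate or a power shortfall.

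**What to change.** Before unblinding, amend SAP 6.3.3.1 and 6.3.3.2 as follows:

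1. For the two co-primary endpoints only, compute the Mantel-Haenszel stratified percentage difference and its test over prophylactic use × onset pain level (four strata).
2. For subjects who dosed before using the eDiary, use the pain level they report for the time of dosing.
3. Keep the by-stratum displays by randomisation stratum only.
4. State that the sparse-cell pooling rule in SAP 6.3 does not apply to these two analyses.
5. State that the secondary endpoints stay on the current two strata despite their cross-reference to 6.3.3.1.
6. Align Protocol 9.4.1.

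No new data are needed. The cost is a few consistency edits across both documents, plus sparse responder counts in the smallest stratum, which Mantel-Haenszel weighting tolerates. If the sponsor prefers not to change the principal analysis, a pre-specified supportive analysis on the four strata is a lighter alternative. It would answer an imbalance question but would not add power to the primary test.
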